7.2 Randomization, blinding and treatment allocation
Randomization will be performed using a dedicated, password protected, SSL-encrypted website. Randomization sequence is generated by a dedicated computer randomization software program, ALEA, using random block sizes (4, 6, up to maximal 8). Due to the nature of the treatment, blinding is not possible.

Patients are randomly assigned in a 1:1 ratio to the 'restricted PEEP'-arm or to the 'liberal PEEP'-arm of this trial.

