APPENDIX IV

Substudy – ‘RELAXECHO’

Background

Cardiac function, in particular of the right ventricle, depends on intrathoracic pressures[1,2]. Use of positive end-expiratory pressure (PEEP) could increase right atrial pressure, pulmonary vascular resistances and right ventricular afterload[3-5]. The net effect of PEEP may be a decrease in right ventricle (RV) volume and output, with no changes in ejection fraction [3]. One small study showed a negative effect of high PEEP on right ventricular strain[6], a surrogate measure of contractility. It is uncertain whether low PEEP has an independent effect on right ventricle myocardial strain. The myocardial performance index (MPI) is regarded as an easy and reproducible echocardiographic parameter of both systolic and diastolic function. The MPI is relatively independent of changes in loading conditions in various clinical settings [8-11]. The RELAX study provides a unique opportunity to study cardiac performance and especially the performance of the right ventricle during varying levels of PEEP (between 0 and 8 cm H₂O) in patients with uninjured lungs.

Aim

The aim of RELAXECHO, a substudy of the RELAX study, is to assess and compare changes in cardiac function as measured by transthoracic echocardiography (TTE) in the two study groups.

Hypothesis

We hypothesize that ventilation with liberal PEEP decreases right ventricular function after 24-48 hours of mechanical ventilation.

Endpoint

The primary endpoint of this sub study is the myocardial performance index of the right ventricle in the first 24-48 hours of mechanical ventilation.

In- and exclusion criteria

Inclusion criteria:

- Admitted to the ICU of the Academic Medical Center
- Enrolled in the RELAX study

Exclusion criteria:

- Ventilation with PEEP > 2 cm H₂O in the 'restricted PEEP'-arm and ventilation with PEEP < 7 cm H₂O in the 'liberal PEEP'-arm
- Refractory circulatory instability requiring > 5 µg/kg/min dopamine or dobutamine, > 1 mg/hour milrinone, or norepinephrine dose of > 0.4 µg/kg/min
- Documented poor left ventricular function (e.g. left ventricular ejection fraction ≤ 30%)

Original sample size calculation

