echocardiographic measures, tissue Doppler imaging (TDI) and speckle tracking echocardiography (STE) parameters will be collected online and with post-acquisition offline analysis[12]. Images of the ventricles are analyzed offline for the myocardial performance index, strain and strain rate and diastolic parameters. Ultrasound clips will be saved for further offline STE analysis and quality control. Measurements will be performed after at least 5 minutes of stable mean arterial pressure. Bidimensional and Doppler measurements will be made in accordance with current recommendations of the American Society of Echocardiography[13].

Statistical analysis

Normally distributed variables are expressed by their mean and standard deviation; non-normally distributed variables are expressed by their medians and interquartile ranges. Categorical variables will be expressed as n (%). To test groups of continuous normally distributed variables, Student's t-test will be used. Likewise if continuous data is not normally distributed the Mann-Whitney U test will be used. Categorical variables will be compared with the Chi-square test or Fisher's exact tests or when appropriate as relative risks. Statistical significance is considered to be at a p-value of 0.05. Where appropriate, statistical uncertainty will be expressed by 95% confidence levels. Analysis will be performed with R (www.r-project.org).

Informed consent

Deferred informed consent from a legal representative is obtained as soon as possibly for this sub study as part of the parent study RELAX. In case a patient is awake and adequate informed consent will be obtained from the patient.

References

3. Pinsky MR. My paper 20 years later: Effect of positive end-expiratory pressure on right ventricular function in humans. *Intensive Care Med*. Springer Berlin Heidelberg; 2014;40:935-41.

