APPENDIX V

Substudy – ‘RELAXLUS’

Background

Ventilation with low PEEP may increase the risk of atelectasis in critically ill patients receiving invasive ventilation, as has been shown before in patients undergoing intraoperative ventilation (1, 2). Lung ultrasound (LUS) is a non-invasive relatively simple bedside technique used to semi-quantify changes in lung aeration in ventilated patients (3), and very capable to detect atelectasis (4).

Aim

The aim of RELAXLUS, a substudy of the RELAX study, is to assess and compare changes in pulmonary aeration and presence of atelectases as detected by LUS in the two study groups.

Hypothesis

We hypothesize that ventilation with restricted PEEP results in a decrease in lung aeration and an increase in atelectases.

Endpoint

The primary endpoint of this sub study is the change in lung ultrasound aeration score in the first 48 hours of invasive ventilation.

In- and exclusion criteria

Inclusion criteria:

- Admitted to the ICU of the Academic Medical Center
- Enrolled in the RELAX study

Exclusion criteria:

- Evidence of cardiac failure or fluid overload, based on an objective assessment such as echocardiography in the medical record and/or on judgment of the treating physician

Methods

LUS is performed at three predefined time points: within 12 hours after enrolment in the RELAX study (this LUS examination is standard of care in patients that are expected to need invasive ventilation > 24 hours), between 24 to 48 hours after enrolment and within the first 24 hours after extubation. Experienced and trained physician will perform LUS examinations, using a 2–5 MHz convex probe. Each

hemithorax is divided into six areas: the anterior, lateral and posterior areas, each divided in upper and lower quadrants, using the parasternal line, the anterior axillary line, the posterior axillary line and the paravertebral line as borders (Figure 1). The 12 regions are examined and a semi-quantitative score is calculated to estimate lung aeration at each time point, and documented in a case report form (see Table 1). Additional sonographic signs previously described for atelectasis will be reported when present for each of the 12 lung regions examined. These include the absence or reduction in lung sliding, the presence of subpleural consolidations and presence of static air bronchograms in consolidated areas (5).

[figure not shown]

Figure 1. Six zones are scanned per hemithorax.

Table 1. LUS aeration score

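### The unqualified statement that blinding is impossible leaves the offline reading of the RELAXECHO primary measure with no provision for masking

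*Protocol*

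**What the plan says.** Protocol section 7.2, whose heading covers blinding, contains one sentence on the subject: "Due to the nature of the treatment, blinding is not possible". It does not separate treating staff from those who read outcomes.

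Appendix IV (RELAXECHO) states: "The primary endpoint of this sub study is the myocardial performance index of the right ventricle", taken at 24 to 48 hours. On the reading it says: "Images of the ventricles are analyzed offline for the myocardial performance index, strain and strain rate and diastolic parameters". It adds: "Ultrasound clips will be saved for further offline STE analysis and quality control". The hypothesis is that liberal PEEP lowers right ventricular function.

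Appendix V (RELAXLUS) states: "The primary endpoint of this sub study is the change in lung ultrasound aeration score in the first 48 hours of invasive ventilation". The procedure differs from the echo substudy: "Experienced and trained physician will perform LUS examinations", and then "a semi-quantitative score is calculated to estimate lung aeration at each time point, and documented in a case report form". No stored clips and no later reading are described. The hypothesis is again directional: less aeration and more atelectasis with restricted PEEP.

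Neither appendix mentions a masked, coded or independent reader. Section 8.2 does hide the identity of the arms in the line listing for the ethics committee, so masking is used elsewhere in the protocol.

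**The concern.** The reason in section 7.2 is true of anyone who sets or sees the ventilator. It is not true of someone measuring an index later from stored images. Because the sentence has no limit and the appendix adds nothing, a site following the protocol has no instruction to mask the RELAXECHO reading, although the workflow already allows it.

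Two further features of Appendix IV make this matter more:

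- Patients are excluded by PEEP level within arm (above 2 cm H₂O in the restricted arm, below 7 cm H₂O in the liberal arm). Whoever applies that rule has to know both arm and PEEP, and no step separates that person from the reader.
- The initial sample-size paragraph defines a dropout as a patient whose index cannot be determined because of poor echogenicity. That is a judgement on the image, so knowledge of the arm could influence who is analysed as well as the value recorded.

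At stake is the credibility of the substudy's primary result. With a small sample and a stated direction, a modest systematic reading difference between arms could be mistaken for a PEEP effect.

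**Working it through.** **1. Is masked reading provided for, and is it feasible?**

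| | Section 7.2 | RELAXECHO (App. IV) | RELAXLUS (App. V) |
|---|---|---|---|
| Statement on blinding | Not possible, because of the treatment | None | None |
| Where the primary measure is read | Not addressed | Offline, from images | Examination scored into a case report form |
| Stored material | Not addressed | Images for offline analysis; clips saved | None described |
| Directional hypothesis | – | Yes | Yes |

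For RELAXECHO the material needed for a masked reading already exists. For RELAXLUS it does not. Both examinations that supply its 48-hour endpoint are also likely to fall during ventilation, when PEEP would normally be visible.

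**2. How sensitive is the RELAXECHO test to a reading difference?** The protocol gives no reader bias, so the shifts below are assumptions.

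Inputs from the sample-size re-calculation in Appendix IV: SD 0.13; target difference 0.12; 18 per group needed; 80% power; two-sided 0.05; 20% added for dropouts (18 × 1.2 = 21.6, hence 22 per group and 44 in total). The planned evaluable number is therefore 18 per group.

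The plan's own figure first: for a difference of 0.12 and SD 0.13, the normal approximation gives 19 per group and the exact t-test 20, against 18 stated. Power at 18 is 79.1% (normal) or 76.7% (t-test). That is close enough to use 18 as the base here.

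False-positive rate with no true effect and a reader shift *b* between arms:

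- SE = 0.13 × √(2/18) = 0.13 × 0.3333 = 0.0433
- Noncentrality = *b* / 0.0433, on 18 + 18 − 2 = 34 degrees of freedom
- Rate = probability that the absolute value of the noncentral t exceeds its two-sided 5% critical value

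| Assumed shift *b* | Share of 0.12 | Noncentrality | Two-sided false-positive rate |
|---|---|---|---|
| 0 | 0% | 0 | 5.0% |
| 0.02 | 17% | 0.46 | 7.3% |
| 0.04 | 33% | 0.92 | 14.6% |
| 0.06 | 50% | 1.38 | 27.0% |

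The normal approximation gives 7.5%, 15.2% and 28.3%. If all 22 per group were evaluable (SE = 0.13 × √(2/22) = 0.0392, 42 degrees of freedom), the rates would be 7.9%, 16.9% and 32.2%.

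No such calculation is made for RELAXLUS, because Appendix V gives no effect size, SD or sample size.

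**The case against.** The strongest reply is that section 7.2 belongs to the main trial, which is an open-label ventilation study, and that read in that setting its sentence is correct. It names neither outcome readers nor substudies, and neither appendix refers back to it. This stands in part: the sentence is true of treatment, and the practical gap lies in the appendices. But it is the only statement on blinding in the protocol and has no limit, so it is reasonable to ask that its scope be stated.

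A reader might infer that both ultrasound measures are read with the arm known. The protocol does not say so. It is silent on what the offline echo readers see, and silence supports only the statement that masking is not provided for.

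A reader might also infer that masking would be equally easy in both substudies. That fails for RELAXLUS, which would need clips saved and a separate scoring session, normally by someone who did not scan the patient.

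The size of any bias is unknown. Appendix IV describes the index as easy and reproducible, and a shift of 0.06 is half the target effect. This objection stands: the table shows sensitivity and does not estimate a bias.

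Finally, both are single-centre substudies listed under other study parameters, and reader instructions could sit in an imaging manual that is not shown. That limits the weight of the point. It does not remove it, because the one statement the protocol does make points the other way.

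**Conclusion.** The point holds for RELAXECHO. The protocol declares blinding impossible for a reason that covers bedside care only, analyses that substudy's primary measure offline under a directional hypothesis, and provides no masked reading. If reading differed between arms by 0.02 to 0.06, the nominal 5% error rate would become about 7% to 27%. Those figures rest on assumed shifts, SD 0.13, 18 evaluable patients per group and no true effect.

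For RELAXLUS the point is weaker: scoring as described appears to be at the bedside, and the reasonable request is that this be acknowledged.

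It would be wrong to extend the point to the main trial. Ventilator-free days and alive at day 28 is not an image reading and is not affected. Nor is any problem shown with the biomarker assays or with the coding of arms in the primary analysis.

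**What to change.** 1. **Section 7.2:** limit the sentence to treating staff.
2. **Appendix IV (RELAXECHO):** state that evaluability and the myocardial performance index are judged offline on coded images and clips, by readers unaware of arm and PEEP. In practice the reader should be someone other than the person who scanned that patient or applied the PEEP-based exclusion.
3. **Appendix V (RELAXLUS):** acknowledge unmasked scoring as a limitation, unless clips can be saved and scored masked with existing staff.

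Item 1 is a change of wording. Item 2 adds a small coding step, and some care in allocating readings, on images already stored. Item 3 costs one sentence, or clip storage and a scoring session if masking is chosen. None of this changes the main trial's endpoint, sample size or conduct.

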7.3 Study procedures

Patients in participating intensive care units (ICU) are screened and randomized within 1 hour after start of mechanical ventilation. Demographic data of all screened patients, regardless of meeting the enrollment criteria will be recorded (age, gender, expected duration of ventilation > or < than 24 hours).

The oxygenation target ranges for SpO₂ and PaO₂ are 92% to 96%, and 8 kPa to 11.5 kPa, respectively.³⁹⁻⁴³ Oxygenation will be maintained in the target ranges primarily by adjusting the FiO₂, which is typically set between 0.21 and 0.6. The oxygenation target is primarily assessed by SpO₂, as measured by pulse oximetry and only in case of discrepancy unreliable reading the oxygenation will be assessed by the PaO₂. Therefore, no extra arterial blood gasses need to be obtained, besides the normally, 3-4 daily conducted arterial blood samples.

7.4 Data collection

- On admission and within the first 24 hours:

- Gender and age (male + years)
- Height and weight (cm + kg)
- Reason for ICU admission
- Reason for ventilation support
- Cause of respiratory failure
- APACHE II score and SAPS II score
- Respiratory status, on admission, and every day at a fixed time point until day 28:
 - Intubation status (if extubated: time of extubation)
 - Tracheostomy status (if tracheostomized: time of tracheostomy)
 - Invasiveness of ventilation (invasive, non-invasive, or intermittent ventilation via tracheostomy)
- Location of patient, every day at a fixed time point until day 28, and at day 90 (in ICU, hospital, other facility, or home) and life status (alive or deceased)
- Pulmonary complication, every day at a fixed time point until day 28 or discharge from ICU, whatever comes first:
 - ARDS (yes or no) (APPENDIX I)
 - Severe hypoxemia (yes or no) (APPENDIX I)
 - Pneumonia (yes or no) (APPENDIX I)
 - Severe atelectasis (yes or no) (APPENDIX I)
 - Pneumothorax (yes or no) (APPENDIX I)
- Need for rescue therapies for severe hypoxemia or severe atelectasis, every day at a fixed time point until day 28 or discharge from ICU, whatever comes first
 - Recruitment maneuver (yes or no) (APPENDIX I)
 - Prone positioning (yes or no)
 - Bronchoscopy for opening atelectasis (yes or no)
- Days with use hemodynamic support, every day at a fixed time point until day 28 or discharge from ICU, whatever comes first. Defined as the number of ICU days with any use of vasopressors/inotropes use for > 1 hour on a day (yes or no)
- Days with use of sedation, every day at a fixed time point until day 28 or discharge from ICU, whatever comes first. Defined as the number of ICU days with any use of sedatives for > 1 hour on a day (yes or no)
- ICU-acquired weakness, every day until day 28 or discharge from ICU, whatever comes first: Medical Research Council (MRC) score (APPENDIX I)⁴⁸

7.4.1. Other data to be collected

- Mechanical ventilation parameters, 1 hour before and 1 hour after randomization and every day at a fixed time point until liberation from the ventilator:
 - Mode of ventilation
 - Tidal volume
 - Respiratory Rate
 - Level of positive end-expiratory pressure (PEEP, cm H₂O)
 - Peak and plateau pressures, or level of pressure support (level above PEEP, and maximal airway pressure, cm H₂O)
 - Inspiration to expiration ratio
 - Inspired oxygen fraction (%)
 - Minute volume (liters/minute)
- Respiratory parameters, 1 hour before and 1 hour after randomization, and every day at a fixed time point until liberation from the ventilator:
 - Peripheral oxygen saturation (%)
 - End-tidal fractions CO₂ (kPa)
 - PaO₂ (kPa)
 - PaCO₂ (kPa)
 - Arterial bicarbonate (mmol/L)
 - Arterial pH
 - Arterial base excess (mmol/L)
- Non-respiratory parameters, every day at fixed time point until liberation from the ventilator:
 - Cumulative fluid balance (ml)
 - Transfusion of blood products (type and ml)
 - Infusion of colloids (type and ml)
 - Infusion of (artificial) colloids (type and ml)
 - Sequential Organ Failure Assessment score (SOFA) score
 - Extra pulmonary infection, sepsis, re-operation, cardiac arrest
 - Therapeutic intervention scoring system (TISS)/ Nursing Activities Score (NAS)

7.5 Withdrawal of individual subject

Subjects can leave the trial at any time for any reason if they wish to do so without any consequences.

7.6 Follow up of subject withdrawn from the study

Patients withdrawn from the trial will not be subjected to follow up.

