4.4 Sample size

Group size calculation is focused on demonstrating non–inferiority. When the sample size in each is 445, an one–sided non–inferiority t–test (targeted at 0.05 significance level) for the difference in means of log–transformed normalized data has a 80% power to reject the null hypothesis that the number of VFD–28 in the 'restricted PEEP'–arm is inferior to the number of VFD–28 in the 'liberal PEEP'–arm by a margin of 10% anticipating on a coefficient of a variation of 0.70 (www.stichting-nice.nl), in favor of the alternative hypothesis that the number of VFD–28 in the 'restricted PEEP'–arm is non–inferior.

The choice for a margin of 10% is motivated by what we consider acceptable from a clinical point of view as the maximal acceptable reduction of the ventilator–free period for non–inferiority. Clinically this margin means that an increase of > 10% in the

duration of mechanical ventilation will reduce the VFD-28 with > 12 hours (calculated over the expected mean duration of mechanical ventilation of 5 days) (<http://www.stichting-nice.nl>) which will be considered inferior. To allow for an anticipated drop out of 10% a total of 980 patients will be included.

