7. METHODS

7.1 Study parameters/endpoints

7.1.1 Main study parameter

The primary endpoint is the number of ventilator-free days and alive at day 28, defined as the number of days from day 1 to day 28; the patient is alive and breathes without assistance of the mechanical ventilator, if the period of unassisted breathing lasted at least 24 consecutive hours.

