7.1.2 Secondary study parameters

Secondary study parameters include:

- ICU length of stay (LOS)
- Hospital LOS
- ICU mortality
- Hospital mortality
- 90-day mortality
- Incidence of development ARDS (APPENDIX I)
- Incidence of severe hypoxemia (APPENDIX I)
- Incidence of severe atelectasis, if a chest radiograph is obtained (APPENDIX I)
- Rescue therapies for severe hypoxemia or severe atelectasis
 - Recruitment maneuver (APPENDIX I)
 - Prone positioning
 - Bronchoscopy for opening atelectasis
- Incidence of pneumothorax, if a chest radiograph is obtained or other kind of imaging suitable for diagnosing pneumothorax is obtained (APPENDIX I)
- Incidence of pneumonia (APPENDIX I)
- The level of PEEP in the 'restricted PEEP'-arm and the 'liberal PEEP'-arm
- Days with use of hemodynamic support, defined as the number of ICU days with any use of vasopressors/inotropes for > 1 hour on a day
- Days with use of sedation, defined as the number of ICU days with any use of sedatives for > 1 hour on a day
- Therapeutic intervention scoring system (TISS)/ Nursing Activities Score (NAS)

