9. STATISTICAL ANALYSIS

9.1 General considerations

The statistical analysis will be based on the intention-to-treat principle. In addition, we will perform a per-protocol analysis to check for robustness of results. The intention-to-treat analysis includes all patients as randomized regardless of whether they received the randomized treatment or other protocol deviations. Per-protocol group analysis only considers those patients who completed the treatment according to the originally allocated protocol. In this non-inferiority trial we include a superiority, primary effect analysis. If the non-inferiority criterion is satisfied, a secondary analysis of the primary endpoint for superiority will be conducted. When appropriate, statistical uncertainty will be expressed by the 95% confidence levels. P-values of 0.05 are used for statistical significance. All statistical analysis will be performed with the R version 3.3.2.

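### Section 7.6 ends follow-up of anyone withdrawn from the trial, which conflicts with an intention-to-treat set of all randomized patients

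*Protocol*

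**What the plan says.** Protocol section 7.6 consists of one sentence: "Patients withdrawn from the trial will not be subjected to follow up". It makes no exception for the primary endpoint or for vital status. Section 7.5 is equally short: "Subjects can leave the trial at any time for any reason if they wish to do so without any consequences". Neither section distinguishes a patient who stops the allocated strategy from one who, personally or through a representative, refuses further data collection.

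Section 9.1 states: "The statistical analysis will be based on the intention-to-treat principle". It defines that set as one that "includes all patients as randomized regardless of whether they received the randomized treatment", and it adds a per-protocol analysis as a robustness check.

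The outcomes need observation over a fixed period. The primary endpoint in section 7.1.1 is "defined as the number of days from day 1 to day 28" on which the patient is alive and breathing unassisted. Section 7.1.2 lists "90-day mortality" as a secondary outcome. Section 7.4 schedules respiratory status daily to day 28, and location and life status daily to day 28 and again at day 90.

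Loss of patients is otherwise dealt with only through the 10% drop-out allowance in section 4.4, which section 7.7 repeats.

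**The concern.** An analysis of everyone as randomized needs an outcome for everyone as randomized. Section 7.6 tells sites to stop collecting that outcome once a patient is withdrawn. Followed as written, it leaves the intention-to-treat set incomplete, and an analysis plan cannot restore data that the protocol says not to collect.

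What is at stake is mainly bias. The trial is unblinded (section 7.2), and section 10.3 expects the arms to differ in their problems: atelectasis and hypoxemia with the lowest PEEP, overdistension and hemodynamic compromise with the higher PEEP. If the decision to leave is influenced by the known allocation or by how the patient is doing, the patients lost from one arm will not resemble those lost from the other. In a non-inferiority comparison, losing patients with poor outcomes from the restricted arm moves the estimate towards non-inferiority.

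**Working it through.** **1. The plan's own sample size.** Inputs from section 4.4: margin 10% (ratio 0.90), coefficient of variation 0.70, one-sided alpha 0.05, power 80%, log scale. Allocation is 1:1 (sections 5.1 and 7.2).

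- Log margin: −ln(0.90) = 0.1054
- Log-scale SD: √ln(1 + 0.70²) = √ln(1.49) = 0.6315
- n per arm = 2 × (1.645 + 0.842)² × 0.6315² / 0.1054², rounded up = 445, which matches the protocol
- Total: 890 × 1.10 = 979, or 490 per arm once 489.5 is rounded up, giving the stated 980. (Dividing 890 by 0.90 would give 989; the difference is immaterial here.)

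**2. Effect of loss on power.** Same inputs, with 980 randomized:

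| Lost | Evaluable | Per arm | Power |
|---|---|---|---|
| 0% | 980 | 490 | 83.3% |
| 2% | 960 | 480 | 82.7% |
| 5% | 931 | 465.5 | 81.6% |
| 10% | 882 | 441 | 79.7% |

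Even if the whole 10% allowance is used up, power is 79.7% against the planned 80%. Power is not the problem.

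**3. Illustration of bias.** The protocol gives no withdrawal rate and no outcomes for withdrawn patients, so both are assumed. Suppose a fraction d of the restricted arm is lost and none of the liberal arm, and the lost patients' geometric-mean VFD-28 is r times that of the observed patients. The restricted arm's full log mean is then its observed log mean plus d × ln(r). The observed comparison is too favorable to the restricted arm by −d × ln(r), and the share of the margin used is −d × ln(r) / 0.1054.

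| d | r | Bias (log) | True ratio ÷ observed ratio | Share of margin |
|---|---|---|---|---|
| 2% | 0.75 | 0.0058 | 0.994 | 5% |
| 2% | 0.50 | 0.0139 | 0.986 | 13% |
| 5% | 0.75 | 0.0144 | 0.986 | 14% |
| 5% | 0.50 | 0.0347 | 0.966 | 33% |

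This uses the log scale of the sample-size calculation. Section 9.2 plans a nonparametric interval for the difference in medians, so the table shows an order of magnitude and does not predict the bias of that estimator.

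**4. What the safeguards do.** The 10% allowance adds patients; it does not make those who remain representative. The per-protocol analysis in section 9.1 is limited to patients who completed treatment as allocated, so it recovers none of the lost outcomes.

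**The case against.** **The sections speak of leaving the trial, not the strategy.** A reader might infer that 7.6 also ends follow-up for patients who merely stop the PEEP strategy. The protocol does not say so. Section 6.4 stops protocol titration under ECMO without withdrawing the patient, section 6.3 moves patients with ARDS to guideline ventilation while ARDS remains a recorded outcome, and section 9.1 keeps patients despite protocol deviations. This objection stands. What is left is that 7.5 and 7.6 do not state the distinction, and that full withdrawal does end follow-up.

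**The route to informative loss is not documented.** Desaturation and instability are handled inside the trial by the rescue provisions of sections 5.2 and 5.3, and 7.5 describes only withdrawal at the subject's wish. Refused or unobtained deferred consent has its own rule of exclusion and replacement (sections 7.7 and 10.2.1), so those patients lie outside this point. Both observations stand. Loss related to arm and prognosis is a possibility in an open trial; the document does not show that it will happen.

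**The size is easily overstated.** A reader might apply the full 10% to withdrawals, assume a 5-day gap between the lost patients of the two arms, obtain 0.10 × 5 = 0.5 day, and equate that with the 12 hours in section 4.4. The documents do not support this. The 10% is a general drop-out allowance, and the 5-day gap has no source. The 12 hours is 10% of an expected 5 days of ventilation, whereas the tested margin is 10% of VFD-28. Take a mean VFD-28 of 18 to 23 days as an assumption: 28 − 5 = 23, and 23 × 0.79 ≈ 18 using the 21% hospital mortality in section 8.2. The margin is then about 1.8 to 2.3 days, and half a day is 22% to 28% of it.

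**Records and consent.** Section 9.4.2 names hospital systems and patient files as sources for costs only, and section 7.4 gives no source for ventilation or life status. Day-90 status of patients at home may not be in hospital records. The consent form is not in the text available for review and may already ask about continued data use. If it does, 7.6 as written contradicts it and still needs rewording.

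**Conclusion.** The conflict is real but narrow. For a patient fully withdrawn before day 28 or day 90, section 7.6 removes the primary outcome or the 90-day vital status that the analysis set in section 9.1 requires, and nothing else in the protocol corrects this. The text does not say that data collected before withdrawal are discarded.

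The size is unknown. Under the stated assumptions (loss in the restricted arm only, lost patients at 50% to 75% of the VFD-28 of those observed), the bias is about 5% to 13% of the log margin at 2% lost and 14% to 33% at 5% lost. Loss that is balanced between arms and unrelated to prognosis would produce no bias of this kind. The consequence for power is negligible. The reason to act is that the possible bias bears directly on the non-inferiority conclusion and is cheap to reduce.

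**What to change.** Reword sections 7.5 and 7.6 to say three things:

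- Stopping the allocated strategy does not end follow-up.
- Anyone who withdraws, or the representative, is asked whether ventilation status to day 28 and vital status to day 90 may still be taken from records. Collection ends only if this is refused.
- These patients are analysed in the arm to which they were randomized.

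The rule for patients without deferred consent is left as it is. The cost is small: changes to protocol and consent wording and one CRF field recording the answer. No visits are added, and refusal is still respected. Outcomes of those who refuse will remain missing, so the change reduces the loss without removing it.
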